### 8.2 Justification of Sample Size

The planned sample size is 50 subjects, which will provide a statistical power of 80% to test against the null hypothesis of endoscopic improvement rate of 12%, at 1-sided significance level of 0.025, assuming the endoscopic improvement rate for PRA023 is 27%.

The null hypothesis of an endoscopic improvement (decrease in SES-CD  $\geq$  50%) rate of 12% is based on a meta-analysis estimate of the upper limit of 95% CI of the observed placebo rate (95% CI) of 9.5% (7.1, 11.9) from multiple modern-era CD clinical trials with centrally read endoscopy and similar eligibility criteria ([Table 7](#)).

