#### **9.2.2 Evaluation of Efficacy Parameters**

The primary efficacy endpoint, endoscopic improvement at Week 12, will be used to assess the efficacy of PRA023. The proportion of subjects in the per-protocol population with endoscopic improvement at Week 12 will be tested against the null hypothesis of 12%, an observed placebo

rate from multiple CD trials. Chi-square test will be used with a 1-sided significance level of 0.025. If significant, the 1st secondary endpoint of proportion of subjects in FAS achieving clinical remission will be tested against the null hypothesis of clinical remission rate of 16% (an observed remission rate for the placebo treated patients from multiple CD trials ([AbbVie 2021](#), [Feagan 2017](#), [Sands 2019](#), [Selinger 2018](#), [Vermeire 2017](#))).

The point estimates for the primary and secondary endpoints will be calculated along with 95% confidence interval for FAS and by CDx status (CDx+ or CDx-).

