3.2 DETERMINATION OF SAMPLE SIZE

The study is planned to enroll approximately 50 subjects. The sample size will enable a statistical power of 80%, at 1-sided significance level of 0.025, to test against the null hypothesis of endoscopic improvement rate of 12%, assuming the endoscopic improvement rate for PRA023 is 27%.

The null hypothesis of an endoscopic improvement (decrease in SES-CD $\geq 50\%$) rate of 12% is based on a meta-analysis estimate of the upper limit of 95% CI of the observed placebo rate (95% CI) of 9.5% (7.1, 11.9) from multiple modern-era CD clinical trials with centrally read endoscopy and similar eligibility criteria. [1]

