6.2.1 PRIMARY ANALYSIS

The proportion of subjects with endoscopic improvement in PP analysis set will be estimated by the number of subjects who achieved the improvement at Week 12 divided by the total number of subjects in PP analysis set. The confidence interval for the proportion will be calculated using Wilson-score method (Wilson 1927). If the resulting lower bound of 95% CI is greater than 12%, the null hypothesis is, therefore, rejected at a 1-sided significance level of 0.025.

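### At 50 subjects no responder cut-off gives both the stated one-sided 0.025 level and 80% power: the Wilson rule (11/50 or more) has a true type I error of 3.25%, and the next cut-off has 73% power

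*SAP*

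**What the plan says.** Sample size. Protocol 8.2 reads "The planned sample size is 50 subjects, which will provide a statistical power of 80"%, for a null endoscopic improvement rate of 12% against an assumed 27%. SAP 3.2 repeats this: "The study is planned to enroll approximately 50 subjects", and "The sample size will enable a statistical power of 80%, at 1-sided significance level of 0.025". Neither section adds subjects for exclusions.

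Test. Protocol 9.2.2: "Chi-square test will be used with a 1-sided significance level of 0.025". SAP 6.2.1 replaces this with an interval rule: "The confidence interval for the proportion will be calculated using Wilson-score method (Wilson 1927"). If the 95% lower bound exceeds 12%, "the null hypothesis is, therefore, rejected at a 1-sided significance level of 0.025". The denominator is the per-protocol (PP) set, which under SAP 5.6 leaves out subjects whose Week 12 SES-CD is missing or cannot be evaluated.

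Neither document gives a responder cut-off, specifies an exact test, or describes 0.025 as a nominal or asymptotic level.

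**The concern.** A one-sample test of a proportion with about 50 subjects can only reject at whole numbers of responders, so its true level moves in steps. A normal-theory rule such as the Wilson bound can land on a step above the nominal level. Whether it does so here decides whether the level claimed in SAP 6.2.1 is true, and whether the 80% power is obtained at that level or by spending more than 0.025.

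This is the only primary efficacy test in a trial whose induction period has no control arm. Under SAP 6.10 it is also the gate to the formal test of clinical remission. One responder can decide the outcome.

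**Working it through.** **Inputs.** N = 50, null rate p0 = 0.12, alternative p1 = 0.27, one-sided 0.025, so z = 1.96 (Protocol 8.2, SAP 3.2). Rule: Wilson 95% lower bound > 0.12 (SAP 6.2.1).

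**1. The plan's power figure.** Normal approximation with the null variance under H0:

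- SE0 = √(0.12 × 0.88 / 50) = 0.0460; SE1 = √(0.27 × 0.73 / 50) = 0.0628.
- Without continuity correction: Φ[(0.15 − 1.96 × 0.0460) / 0.0628] = Φ(0.954) = 83.0%.
- With correction 1/(2N) = 0.01: Φ[(0.14 − 1.96 × 0.0460) / 0.0628] = Φ(0.795) = 78.7%.

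The stated 80% lies between these, so it is reproduced as an approximation.

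**2. The cut-off that the Wilson rule implies.** With p = x/n,

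L = [p + z²/(2n) − z√(p(1−p)/n + z²/(4n²))] / (1 + z²/n).

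- 10/50: L = 11.24%, do not reject.
- 11/50: L = 12.75%, reject.

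The uncorrected score (chi-square) statistic gives the same cut-off: (0.20 − 0.12)/0.0460 = 1.74 for 10/50 and (0.22 − 0.12)/0.0460 = 2.18 for 11/50.

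**3. Exact properties of each cut-off at N = 50**, from P(X ≥ c) with X binomial(50, p):

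| Reject from | Type I error (p = 0.12) | Power (p = 0.27) | Wilson lower bound | Clopper-Pearson lower limit |
|---|---|---|---|---|
| 10 | 7.08% | 90.2% | 11.24% | 10.03% |
| 11 (SAP rule) | 3.25% | 83.0% | 12.75% | 11.53% |
| 12 | 1.35% | 73.3% | 14.30% | 13.06% |

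Both error and power fall as the cut-off rises. Twelve is therefore the lowest cut-off that keeps 0.025, and its power is below 80%. No cut-off at 50 has both properties. A continuity-corrected Wilson bound for 11/50 is 11.99%, which also moves the cut-off to 12.

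**4. Other PP sizes.** The documents give no exclusion rate, so 40 to 50 is an assumed range.

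| PP size | Wilson cut-off | Exact level | Power | Exact-test cut-off | Exact level | Power |
|---|---|---|---|---|---|---|
| 40 | 9 | 4.43% | 79.1% | 10 | 1.75% | 67.0% |
| 41 | 9 | 5.09% | 81.6% | 10 | 2.07% | 70.3% |
| 42 | 10 | 2.43% | 73.3% | 10 | 2.43% | 73.3% |
| 43 | 10 | 2.84% | 76.2% | 11 | 1.09% | 64.0% |
| 44 | 10 | 3.29% | 78.8% | 11 | 1.30% | 67.3% |
| 45 | 10 | 3.79% | 81.2% | 11 | 1.54% | 70.4% |
| 46 | 10 | 4.34% | 83.4% | 11 | 1.81% | 73.3% |
| 47 | 11 | 2.12% | 76.0% | 11 | 2.12% | 76.0% |
| 48 | 11 | 2.45% | 78.5% | 11 | 2.45% | 78.5% |
| 49 | 11 | 2.83% | 80.9% | 12 | 1.15% | 70.5% |
| 50 | 11 | 3.25% | 83.0% | 12 | 1.35% | 73.3% |

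The Wilson rule exceeds 0.025 at 8 of these 11 sizes; the simple mean of its level is 36.86/11 = 3.35%. Where it keeps the level (42, 47, 48), power is below 80%. The same failure to meet both continues at 51 and 52.

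**5. Where both properties first hold.** Exact test: 53 analysed subjects (12/53: level 2.12%, power 80.6%). Wilson rule: 54 (12/54: 2.44%, 82.7%). Neither is monotone: at 55 the Wilson level is 2.79% and the exact test's power is 75.9%. From 57 to 71, the largest size checked, the exact test has at least 80% power at every size.

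**The case against.** The strongest reply is that nothing was miscalculated. The Wilson bound and the chi-square test are accepted approximate methods, 0.025 is their nominal level, the two documents carry it consistently, and 80% is reproduced by a standard formula. The excess at 50 subjects is 0.75 percentage points, due to discreteness. An exact test is conservative there, using 1.35% of the 2.5% allowed. The trial is an open-label phase 2a proof of concept, and 12% is meant as an upper bound on placebo response: at the tabled simple average of 10.7%, 11 or more of 50 would occur 1.5% of the time. At 50 subjects the two rules disagree only if exactly 11 respond.

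Much of this is fair. The 80% is not wrong by itself, and the Wilson rule as planned exceeds it. A level of twice nominal arises only at 41 subjects, which needs 9 of 50 excluded (18%); at 42, 47 and 48 the level is kept. Choosing an exact test is partly a matter of preference.

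It does not remove the point. The stated level refers to a true rate of 12%, and at that rate it is not met at 50. SAP 6.2.1 gives 0.025 as the level of rejection without qualification. The 80% power depends on the step that overspends it.

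**Conclusion.** The concern holds. With 50 analysed subjects, the SAP rule has a true one-sided type I error of 3.25% and power of 83.0%. A rule that respects 0.025 has 73.3% power. Level and power as stated together are not available at 50, nor at any analysed size from 40 to 52.

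The figures at 50 follow exactly from the plan's own inputs and an uncorrected Wilson interval. The spread across PP sizes rests on the assumed range of 40 to 50, and all figures would change if the 12% null were revised. The excess is modest. It should be corrected because it concerns the sole primary efficacy test, but it does not invalidate the design.

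**What to change.** In SAP 6.2.1 and Protocol 9.2.2, base rejection on the exact binomial test: the Clopper-Pearson 95% lower limit must exceed 12% at the actual PP size. That means at least 12 responders at 50, and 11 at 45 to 48. Keep the Wilson interval for display if wanted. In Protocol 8.2, the Protocol synopsis and SAP 3.2, restate power as about 73% for 50 analysed subjects, and say that it varies with PP exclusions (70.4% at 45, 78.5% at 48).

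If the Wilson rule is kept, call 0.025 nominal and state the exact level: 3.3% at 50, and the value for the achieved PP size in the report. If the null is revised, recompute all of these.

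The cost is wording in both documents, a less favourable stated power, and one more responder needed at 50. No extra patients are required. To restore both properties under the exact test instead, the sponsor would need 53 analysed PP subjects, or at least 57 to avoid the dip at 55 and 56, and would have to enrol above those numbers to cover exclusions.

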6.2.2 SENSITIVITY ANALYSIS

In the sensitivity analysis, patients in FAS with missing SES-CD score at Week 12 will be considered as a non-responder for the endpoint of endoscopic improvement. The 95% confidence interval will then be calculated according to Wilson score method.

The proportion of subjects with endoscopic improvement for PP analysis set and associated 95% confidence intervals will also be estimated by the following subgroups:

- CDx status (CDx+ or CDx-)
- Number of prior biologic use (0, 1, or 2+)
- Disease extent (ileal only, colonic only, or both)
- Disease severity (baseline SES-CD ≤ 16, or > 16)
- Concomitant use of immunosuppressive including AZA, 6MP, and MTX (Yes, or No)
- Concomitant use of oral corticosteroids (Yes, or No)
- ADA status (positive, negative)

Given the small sample size of the trial, the results of subgroup analysis should be interpreted with caution. The forgoing analysis may be modified when the sample size in a subgroup is deemed too small.

6.3 SECONDARY EFFICACY ENDPOINTS

6.3.1 DICHOTOMOUS OR BINARY ENDPOINTS

The definition of the dichotomous secondary efficacy endpoints (i.e., responders) are listed in Table 3 below.

Table 3 Definition of Secondary Binary Endpoints

Outcome	Measure	Definition	Analysis Timepoints
Clinical Remission	CDAI	Crohn's disease activity index [CDAI] < 150	Week 12
Endoscopic and clinical improvement	SES-CD and CDAI	Decrease in SES-CD ≥ 50% AND reduction in CDAI ≥ 100 points from Baseline, or CDAI < 150	Week 12
Biomarker and Clinical Composite Improvement	hsCRP and CDAI	Decrease in hsCRP or fecal calprotectin ≥ 50% from Baseline and reduction in	Week 12

		CDAI \geq 100 points from Baseline, or CDAI < 150	
Clinical Response	CDAI	Reduction in CDAI \geq 100 points from Baseline or CDAI < 150	Week 12
PRO-2 remission	Abdominal pain score and Stool frequency	Average daily abdominal pain score \leq 1 point and average daily stool frequency \leq 3 points with abdominal pain and stool frequency no worse than Baseline	Week 12
Normalization of hsCRP	hsCRP	hsCRP < ULN, among subjects whose baseline hsCRP \geq ULN	Baseline, Week 12
Normalization of fecal calprotectin	fecal calprotectin	fecal calprotectin < ULN, among subjects whose baseline fecal calprotectin \geq ULN	Week 12
Anti-drug antibody (ADA) and Neutralizing antibody (Nab)	ADA and Nab	Positive ADA at any time; Positive Nab at any time	Over time

Abbreviations: SES-CD, Simple endoscopy score for Crohn's disease; CDAI, Crohn's disease activity index; hsCRP, High sensitivity C-reactive protein; PRO-2, Two component patient-reported outcome; ADA, Anti-drug antibody; Nab, Neutralizing antibody.

The proportion of clinical remission in FAS will be analyzed according to the method similar to the sensitivity analysis for the primary efficacy endpoint, in the case of missing data in CDAI at Week 12. If the resulting lower limit of 95% confidence interval is greater than 16%, the observed remission rate for the placebo treated patients from multiple prior CD trials ([1], [7], [8], [9], [10]), the null hypothesis for the first secondary endpoint of clinical remission at Week 12 will be rejected at a 1-sided significance level of 0.025.

The point estimate and 95% CI for the secondary efficacy endpoints will be calculated for FAS, while the missing values in the categorical endpoint will be imputed as non-responders. Subgroup analysis (defined in section 6.2.2) may be performed for clinical remission, endoscopic and clinical improvement, biomarker and clinical composite improvement, clinical response, and PRO-2 remission.

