#### 3.2 Secondary Endpoints

- The proportion of subjects in clinical remission (CDAI < 150) at Week 12
- The proportion of subjects with endoscopic and clinical improvement, as defined by decrease in SESCD  $\geq 50\%$  AND reduction in CDAI  $\geq 100$  points from Baseline at Week 12
- The proportion of subjects with both biomarker and clinical improvement (decrease in hsCRP OR fecal calprotectin  $\geq 50\%$  from Baseline, among subjects with at least one elevated biomarker at Baseline, AND reduction in CDAI  $\geq 100$  points from Baseline) at Week 12
- The proportion of subjects with normalization of hsCRP (as defined by hsCRP < ULN), among subjects with elevated concentrations at Baseline, at Week 12
- The proportion of subjects with normalization of fecal calprotectin (as defined by fecal calprotectin < ULN), among subjects with elevated concentrations at Baseline, at Week 12
- The proportion of subjects in clinical response, as defined by reduction in CDAI  $\geq 100$  points from Baseline at Week 12
- The proportion of subjects with PRO-2 remission (defined as average daily abdominal pain score  $\leq 1$  point and average daily stool frequency  $\leq 3$  points with abdominal pain and stool frequency no worse than Baseline) at Week 12
- Change in SES-CD score at Week 12 from Baseline
- Descriptive summaries of PK and immunogenicity of PRA023
- Proportion of subjects developing anti-drug antibody (ADA) and neutralizing antibody (Nab)

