2 STUDY OBJECTIVES AND ENDPOINTS

This is a Phase 2a, Multi-Center, Open-Label Study to Evaluate the Safety, Efficacy, and Pharmacokinetics of PRA023 in Subjects with Moderately to Severely Active Crohn’s Disease. The primary, secondary and exploratory study objectives and corresponding endpoints for IP analyses are listed in **Table 1** below.

Table 1 Study Objectives and Endpoints

Objectives	Endpoints
Primary	
To evaluate the safety and tolerability of PRA023 following 12-weeks of induction therapy	
 Proportion of subjects reporting AEs, SAEs, AEs leading to discontinuation, and markedly abnormal laboratory values
To assess the proportion of subjects with endoscopic improvement (decrease in simple endoscopy score for Crohn’s disease [SES-CD] \geq 50% from Baseline) at Week 12	
 Proportion of subjects with endoscopic improvement , as defined by decrease in SES-CD \geq 50% from Baseline at Week 12
Secondary	
To assess the proportion of subjects with clinical remission (Crohn’s disease activity index [CDAI] < 150) at Week 12	
 Proportion of subjects in clinical remission (CDAI < 150) at Week 12
To assess the proportion of subjects with endoscopy and clinical improvement at Week 12	
 Proportion of subjects with endoscopic and clinical improvement, as defined by decrease in SES-CD \geq 50% AND reduction in CDAI \geq 100 points from Baseline or CDAI <150 at Week 12
To assess the proportion of subjects with biomarker and clinical improvement, among subjects with at least one elevated biomarker at Baseline, at Week 12	
 Proportion of subjects with both biomarker and clinical improvement (decrease in hsCRP OR fecal calprotectin \geq 50% from Baseline, among subjects with at least one elevated biomarker at Baseline, AND reduction in CDAI \geq 100 points from Baseline or CDAI <150) at Week 12

To assess the proportion of subjects with normalization of C-reactive protein (hsCRP < upper limit of normal [ULN]), among subjects with elevated concentrations at Baseline, at Week 12	
 Proportion of subjects with normalization of hsCRP (as defined by hsCRP < ULN), among subjects with elevated concentrations at Baseline, at Week 12

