6.8 MISSING DATA HANDLING

6.8.1 NON-RESPONDER IMPUTATION (NRI)

For the responder analyses as described in Table 3 of Section 6.2, unless specified otherwise, subjects who do not have sufficient measurements to determine the endpoint will be considered as non-responders (i.e., non-responder imputation (NRI)). Specifically, all subjects who discontinue from the study at any time prior to the assessment timepoint (regardless of reason) or fail to have an adequate efficacy assessment at that timepoint will be considered a non-responder.

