10 CHANGES FROM PROTOCOL

Methods in this SAP different from the methods described in the protocol are summarized as follow:

- In Section 2, for objectives and endpoints that has accessing timepoint at Week 50, all timepoints at Week 50 were removed from this SAP. The final analysis of OLE data will be specified in a separate SAP.

- In Section 2 and Section 3.1, the definition for clinical response is refined so that responders will also include those patients who achieve clinical remission (CDAI < 150) but may not achieve ≥ 100 point reduction in CDAI from baseline.
- In section 2, additional exploratory endpoints (endoscopic remission, ulcer-free at Week 12, change in SES-CD segment score from baseline to week 12, clinical improvement by PRO-2 score, IBDQ remission or response,(steroid-free clinical remission for CDAI and by PRO-2, steroid-free clinical improvement by CDAI and by PRO-2, Clinical response by PRO-2 total score,) were add in the overall objectives and endpoints.
- In section 2, serum PD marker EHI was removed from the SAP. It will be analyzed when it becomes available.
- For analysis populations, PP analysis set was added.
- For evaluation of primary efficacy endpoint, the analysis specified in SAP V01 based on the method of multiple imputation was removed due to the known lack of sufficient correlation between SES-CD and CDAI scores in prior CD clinical trials. Instead, PP analysis set, which requires evaluable endoscopic score at Week 12, will be used and the confidence interval for the proportion will be calculated using Wilson-score method.
- Sensitivity analysis based on FAS was added to further access the robustness of primary analysis.
- For evaluation of secondary efficacy dichotomous or binary endpoint, the confidence interval for the proportion will be calculated using Wilson-score method, while non-responder imputation may apply for missing endpoint.
- For evaluation of the continuous secondary efficacy endpoint, PP analysis set and ANCOVA will be used for the change from baseline in SES-CD at Week 12. The median for the change from baseline in SES-CD score at Week 12 for PP analysis set will also be estimated and p-value for testing against no change will be reported using Wilcoxon rank test
- For evaluation of continuous exploratory efficacy endpoints, endpoints with multiple assessments over time, MMRM will be used. The 95% confidence interval for the LS mean for the change from baseline at Week 12 will be calculated.

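### Two secondary composites in the SAP are written without brackets, so on a literal reading CDAI below 150 alone counts as success; context points to the stricter rule, which should be written out

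*SAP*

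**What the plan says.** SAP Section 6.3.1, Table 3 gives the responder definitions for the binary secondary endpoints. The row for endoscopic and clinical improvement reads "Decrease in SES-CD ≥ 50% AND reduction in CDAI ≥ 100 points from Baseline, or CDAI < 150". The next row, the biomarker and clinical composite, ends with the same comma and the same CDAI alternative.

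SAP Section 2, Table 1 introduces the first composite as "Proportion of subjects with endoscopic and clinical improvement, as defined by decrease in SES-CD" and closes it with "100 points from Baseline or CDAI <150 at Week 12", again without brackets and here without the comma. The biomarker composite in Table 1 is built in the same way, but is limited to subjects with at least one biomarker elevated at baseline. Table 3 does not repeat that limit.

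SAP Section 10 explains where the added clause came from: "the definition for clinical response is refined so that responders will also include those patients who achieve clinical remission (CDAI < 150"), even if they do not fall by 100 points. It lists no change to the endoscopic or biomarker half. Protocol Section 3.2 also has this endpoint ("The proportion of subjects with endoscopic and clinical improvement, as defined by decrease in" SES-CD) and requires both the SES-CD decrease and the 100-point CDAI fall, with no route through CDAI below 150.

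For missing data, SAP Section 6.8.1 says that "subjects who do not have sufficient measurements to determine the endpoint will be considered as non-responders".

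**The concern.** A condition of the form A AND B, or C is normally evaluated with AND first, giving (A AND B) OR C. The comma before the last clause in Table 3 supports that grouping. In SAP Table 4, the enhanced PRO-2 response row uses a comma in the same way, to set off the outermost condition. A programmer working from Table 3 could therefore code CDAI below 150 as sufficient by itself.

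An endpoint meant to show joint endoscopic and clinical benefit would then count every clinical remitter, whatever the endoscopy showed. The biomarker composite would likewise count remitters with no biomarker fall.

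Missing data are affected too. Under the literal rule, CDAI below 150 already determines the endpoint, so a subject with no Week 12 endoscopy could be counted as an endoscopic-and-clinical success. The second sentence of Section 6.8.1, on subjects without an adequate efficacy assessment, might prevent this, but it does not say which assessment is meant for a composite.

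The study has one arm in the induction period. These rates are reported on their own with 95% intervals, and possibly by subgroup including CDx status, so no concurrent control would absorb an inflated definition.

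**Working it through.** The documents state no expected rate, null value or power for either composite, so there is no figure to reproduce. The check compares the two readings.

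**Notation.** A = SES-CD decrease of at least 50%; B = CDAI reduction of at least 100; C = CDAI below 150.

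- Literal: L = (A AND B) OR C
- Bracketed: K = A AND (B OR C)

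**Where they differ.** If A holds, both reduce to B OR C. If A fails, L reduces to C and K is a failure. The readings disagree only in subjects with C and not A, so:

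- P(L) − P(K) = P(C and not A)
- P(L) ≥ P(C) and P(K) ≤ P(A), whatever the dependence
- under independence the gap is P(C) × (1 − P(A)); its possible range is max(0, P(C) − P(A)) to min(P(C), 1 − P(A))

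**At the documents' null rates.** P(A) = 12% (SAP Section 3.2) and P(C) = 16% (protocol Section 9.2.2; SAP Section 6.3.1).

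- Literal rate at least 16%; bracketed rate at most 12%
- Gap under independence: 0.16 × 0.88 = 0.141; 0.141 × 50 ≈ 7 subjects
- Range: 0.16 − 0.12 = 4% up to 16%

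**At the planning rate.** P(A) = 27% (SAP Section 3.2). The documents give no remission rate for PRA023, so 16% to 50% is assumed.

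| Assumed P(C) | Gap under independence, 0.73 × P(C) | Of 50 | Possible range |
|---|---|---|---|
| 16% | 11.7% | about 6 | 0–16% |
| 30% | 21.9% | about 11 | 3–30% |
| 40% | 29.2% | about 15 | 13–40% |
| 50% | 36.5% | about 18 | 23–50% |

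**Ratio of the two rates.** This needs two more assumptions: P(B OR C) is 15 points above P(C), and the endoscopic and CDAI outcomes follow a latent bivariate normal with correlation 0.1 to 0.3. In the table, the first value in each pair is for 0.1.

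| Assumed P(C) | Bracketed | Literal | Ratio |
|---|---|---|---|
| 16% | 10%, 12% | 20%, 21% | 2.14, 1.75 |
| 30% | 13%, 16% | 34%, 34% | 2.54, 2.13 |
| 40% | 16%, 19% | 44%, 44% | 2.73, 2.35 |
| 50% | 19%, 21% | 54%, 54% | 2.88, 2.54 |

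**How much the stated refinement should matter.** Entry requires CDAI of 220 to 450. From a baseline of 250 or more, reaching CDAI below 150 already means a fall of more than 250 − 150 = 100 points. Under the bracketed reading, the added clause therefore brings in only endoscopic improvers with a baseline from 220 to just under 250. The literal reading waives endoscopy for every remitter, which goes far beyond the change that Section 10 describes.

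**Biomarker composite.** The same algebra applies, with A replaced by the biomarker fall. The documents give no rate for that event, so the gap is not quantified.

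**The case against.** The strongest reply is that the context already settles the meaning. Table 1 and the Clinical Response row of Table 3 define clinical improvement itself as B OR C, so endoscopic and clinical improvement is naturally A AND (B OR C). Table 3 lists both SES-CD and CDAI as the measures of the first composite, and Table 1 says that both biomarker and clinical improvement are required. Section 10 widens only clinical response, and the protocol requires both halves. Strict precedence also proves too much: in the biomarker row it would split hsCRP from fecal calprotectin and make an hsCRP fall alone a success, which nobody would intend.

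This stands as evidence of intent. A reader might infer from Table 3 that the SAP has made CDAI below 150 sufficient by itself. The documents do not support that as the settled rule, because no section says that remission alone is enough. But no section gives the bracketed form either, and Table 3 is the definition a programmer would use.

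It is also fair that the composites carry no hypothesis test. SAP Section 6.10 covers only the primary endpoint and clinical remission, and entry to the extension depends on clinical response, not on these composites. That limits the consequence; it does not remove the ambiguity from two reported secondary endpoints.

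**Conclusion.** The concern holds as an ambiguous definition that could be programmed either way, with materially different results. The intended rule is very probably A AND (B OR C).

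The firmest statement of size needs no assumption about correlation: at the documents' null rates, the literal reading gives at least 16% and the bracketed reading at most 12%. The 14-point gap (7 of 50) adds independence. The ratio of roughly 1.8 to 2.9 rests on 27% endoscopic improvement, an assumed remission rate of 16% to 50%, response 15 points above remission and a correlation of 0.1 to 0.3. A reader might infer a flat two- to three-fold inflation. That describes the assumed 30% to 50% remission cases, and arises only if the literal rule is programmed.

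The primary analysis, the clinical remission test and the power statement are untouched. What is at stake is the point estimates, 95% intervals and any subgroup results for the two composites. The change should be made, but the trial's formal conclusion does not depend on it.

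**What to change.** In SAP Tables 1 and 3, write:

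- Endoscopic and clinical improvement: SES-CD decrease ≥ 50% AND (CDAI reduction ≥ 100 points OR CDAI < 150).
- Biomarker and clinical improvement: (hsCRP decrease ≥ 50% OR fecal calprotectin decrease ≥ 50%) AND (CDAI reduction ≥ 100 points OR CDAI < 150), among subjects with at least one elevated biomarker at Baseline.

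The restriction in the second definition must stay in Table 1 and be added to Table 3, so that bracketing does not change the denominator. With the first definition in place, a subject with no Week 12 SES-CD score cannot meet the endpoint and is a non-responder under Section 6.8.1 without further wording.

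The cost is a few brackets and one repeated phrase, plus a check that the programming specification matches. No data collection, sample size or test changes. Under SAP Section 1, a change after finalization is recorded with its rationale in the clinical study report.
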